4.3.2 Recruitment from other community settings

Contact has been made with the county council leads for libraries, wellbeing hubs, all pharmacies and all children's centres in Warwickshire, and with the family information service and the registrar's office in order to provide information about the proposed study and gain in principle agreement to support recruitment. We have so far gained in principle support from four pharmacies, over 30 children's centres, all seven wellbeing hubs, the family information service and the registrar's office and will be acting on further suggestions from our PPI group for community recruitment locations (e.g. dentists). Following suggestions from our PPI group, we will also be including bus stop and bus based advertising to aid recruitment.

We will supply each participating community setting with posters to display in prominent locations advertising the 'MyWay' study with contact details of the research team and a community-setting specific QR code to gain immediate access to the study website for participants. We will train all staff in participating locations about the study to enable them to answer any basic queries and to promote it confidently. We will also combine staff promotion of the study via leaflets and a very brief verbal introduction with ad hoc research assistant presence for active promotion and recruitment on site. Where staff provide a leaflet, access to the study will be either through QR code/web link to project website or via contact with the research team. Where a research assistant recruits on site, physical copies of the participant information sheet will be available and immediate access provided to the study via tablet computers. People will have the option to gain access to the study but consider participation and return later to the website to provide informed consent.

4.3.3 Online recruitment

The marketing and communications team at Warwickshire County Council (WCC) will be supporting all online recruitment activities. Specifically, they will provide support for online promotion of the study via social media, targeted email marketing, Google advertising and all WCC internal and external channels such as press releases and electronic newsletters. Social media will include Facebook ads as well as via their standard social media channels including twitter feed, Facebook pages and web pages. These ads will appear to anyone in the Warwickshire area searching for health-related products or services. We will run a three-month long campaign to advertise the study. In addition, participating community settings including children's centres, pharmacies and wellbeing hubs will also promote the study online via their communication channels including social media such as Facebook and twitter. Anyone hearing about the study via this method will be able to link directly to the study website.

4.4 Inclusion Criteria

All smokers over the age of 16 years and either 1) registered with a participating GP practice in Warwickshire or 2) who self identifies as eligible for study participation and responds to study promotion via community settings or online, will be eligible to participate. We will not ask those under 16 years of age. It does not matter whether participants have previously attended a SSS or not. Participants need to have access to the internet via a computer or smartphone to create a participant account in the study software, complete study measures and view the StopApp or control content,

and a mobile phone and/or email address for the receipt of SMS reminders to attend an appointment.

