3.3 Secondary Objectives

Secondary objectives of the feasibility trial are to estimate the:

- **3.3.1** acceptability of randomisation and the StopApp intervention for participants
- **3.3.2** acceptability of primary and secondary outcome measures and measures required for cost-effectiveness and cost utility analyses in a future trial
- **3.3.3** key costs which would be incurred in delivering the intervention and usual care, including a comparison of non-attendance at SSS (Did-not-attend or DNA rates) between each arm of the trial.
- **3.3.4** feasibility of accessing SSS and GP data (if recruited via GP) on attendance, quit dates set and four-week quits for trial participants
- **3.3.5** any differential recruitment and attrition rates across socio-economic groups and age and gender
- **3.3.6** rate of SSS attendance in the treatment and control groups to estimate the event rate of the primary outcome measure for a future trial and support future trial sample size calculations

4. Methodology

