4.5 Exclusion Criteria

Via self-assessment, smokers who do not understand written English or are under 16 years of age, will be excluded from taking part.

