4.7 Intervention

The StopApp is a web-based self-administered interactive intervention designed to address the barriers that smokers typically face in accessing SSSs. In brief, the intervention comprises 1) an introduction to StopApp. 2) collection of information about age, gender, previous attempts to guit and previous use of SSSs in order to tailor content accordingly. Age and gender are used to provide messaging from similar others to enhance perceptions that 'people like me use SSS'. Information about previous guit attempts and use of SSSs is used to tailor the way in which the subsequent content is framed, 3) StopApp then provides users with information about what SSSs are like, to address negative perceptions many smokers have about what the service offers and how they will be treated. Infographics and messages from real SSS users are used to try to keep textual information minimal and enhance positive norms about who uses SSS. 4) Throughout engagement, the option to go straight to booking an appointment is provided in case people are already motivated to do this. 5) Users are then provided with a list of other potential barriers to SSS access that they may have and can select as many as apply. This then determines which further content is supplied which addresses 6) practical barriers 7) fears about trying and failing and 8) beliefs that needing support to stop smoking is a 'weakness'. At the end of the process users have the option to either 9) book an appointment or 10) get a reminder to re-access the intervention one month later, if they feel they are not yet ready. We have appended an example route through the StopApp (see Appendix F) to illustrate the content. It is linked to the on-line outcomes reporting systems (PharmOutcomes and Outcomes4Health) used by SSSs in Warwickshire (and many other local authority areas across the UK). PharmOutcomes is used by pharmacists and others offering stop smoking services. Outcomes4Health is used by GP practices offering SSS appointments. These secure systems support service providers in recording information about what they have provided to a service user and the outcomes associated with this, including whether or not a quit date was set and whether or not a CO verified 4 week guit rate was achieved by a service user.

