We will receive data for each of our participants who consented from PharmOutcomes and Outcomes4Health on whether or not they booked an appointment, whether or not they attended an appointment, whether or not they set a quit date and whether or not they achieved a 4 week quit including whether or not this was CO verified. The stop smoking service data will be sent to a secure NHS.net email address held by one member of the research team, in report format, and will include only trial participants who consented to the research team being sent information about their SSS use. This data will be recorded by hand by a researcher directly into a spreadsheet alongside each participant's unique ID generated by eNgage. Each participant's name will be used to link the data (unique ID and stop smoking data) but will not be recorded within the database. Coventry University is currently developing a data sharing agreement with Warwickshire Public Health and Pinnacle Health for this purpose. Recruitment will not begin until this (as well as all other ethics and governance approvals) is in place.

A drop-down box within the Pharmoutcomes/Outcomes4Health appointment data input form used by SSS staff, will include a compulsory prompt to staff to ask whether their client is taking part in the MyWay research project/study (with details of the trial to help recall). If the client answers yes, they will be asked if they agree (consent) to the researcher's contacting the service to collect information about their use of the service, with a 'YES/NO' drop-down box. This acts as a proof of participant consent for Pinnacle health, in order to generate a report of trial participants who provide consent only.

Downloaded data - on completion of data collection, the following will occur:

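### A booking or service contact that predates randomisation can count as an event, inflating both arms' rates and diluting the difference passed to the definitive trial

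*Protocol*

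**What the plan says.** On entry, section 4.4 of the protocol admits smokers of eligible age and states: "It does not matter whether participants have previously attended a SSS or not". Under section 4.5, "smokers who do not understand written English or are under 16 years of age, will be excluded from taking part"; there are no other exclusions. Neither section separates a past service user from someone who has an open appointment or is being supported at entry. Section 4.10.1 lists earlier SSS use among the baseline items, but not current use or an open booking.

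On where participants come from, sections 4.3.1 and 4.3.2 recruit through four GP practices and through community sites, including pharmacies: "We have so far gained in principle support from four pharmacies". Section 4.7 describes both as types of service provider: "PharmOutcomes is used by pharmacists and others offering stop smoking services", and "Outcomes4Health is used by GP practices offering SSS appointments".

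On outcomes, section 4.9.2 says that the service report will show "whether or not they booked an appointment, whether or not they attended an appointment", followed by quit dates and 4-week quits. No dates of booking or attendance are listed. The two-month questionnaire in 4.10.2 asks about the same events and also asks what prompted the booking.

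On use of the data, objective 3.3.6 is to estimate the "rate of SSS attendance in the treatment and control groups to estimate the event rate of the primary outcome measure for a future trial" and to support its sample size. Section 4.12 uses the observed difference between arms in bookings and attendance for the same purpose.

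**The concern.** StopApp and the leaflet are meant to prompt smokers to make a new approach to the service; the protocol's background speaks of obtaining a first appointment and of reaching smokers not now reached. A participant who is already booked, has been seen but not yet reached a quit date, or has lapsed while still in contact can be a current smoker and so eligible. That person's booking cannot result from either arm's material. Under the outcome wording it still registers as a booking, and usually as an attendance if the appointment is kept.

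Such participants add events that do not depend on allocation. They raise the control rate, which feeds the variance in a two-proportion sample size, and they shrink the observed difference. Both push the definitive sample size upward. The comparison of non-attendance in 3.3.3 is exposed in the same way.

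**Working it through.** **The plan's own figures.** Section 4.11 gives 980 smokers for a 7-point difference, 1.8 recruits per day and a feasibility sample of 162. The linked figures reproduce: 980 / 540 days = 1.81 per day; 1.8 × 90 = 162; 162 / 3 = 54 per setting. The 980 cannot be reproduced from stated inputs, because the protocol gives no control rate, power or significance level for it. With no dropout, a two-sided 5% test and no continuity correction, a 7-point difference comes within 3% of 980 for control rates of about 9.3–10.1% at 90% power or 14.7–16.1% at 80% power. A control rate of 10% is therefore a reasonable illustration, but it is an assumption.

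**Inputs.**
- Difference of 7 points: section 4.11.
- 1:1 allocation: section 4.6, so about 162 / 2 = 81 per arm.
- True rates of 10% and 17%: assumed.
- c, the share of entrants with service contact at entry: not in the protocol, so varied from 0 to 10%.
- All such entrants counted as attenders: assumed, an upper bound.

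**Formulae.** Observed rate in an arm = c + (1 − c)p. Observed difference = (1 − c)(p1 − p0). Share of all events that come from existing contacts = c / [c + (1 − c) × 0.135], where 0.135 is the mean of 0.10 and 0.17. Sample size per arm is the usual two-proportion formula with pooled variance under the null, two-sided 5%:

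n = [1.96 √(2p̄(1 − p̄)) + z √(p0(1 − p0) + p1(1 − p1))]² / (p1 − p0)², with z = 0.842 for 80% power and 1.282 for 90%.

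| c | Control | Intervention | Difference (points) | Events from existing contacts | n per arm, 80% power | Total N, 90% power |
|---|---|---|---|---|---|---|
| 0 | 10.0% | 17.0% | 7.00 | 0 | 373 | 998 |
| 1% | 10.9% | 17.8% | 6.93 | 7% | 401 | 1074 |
| 2% | 11.8% | 18.7% | 6.86 | 13% | 430 | 1150 |
| 5% | 14.5% | 21.2% | 6.65 | 28% | 519 | 1388 |
| 10% | 19.0% | 25.3% | 6.30 | 45% | 681 | 1822 |

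At c = 5%, for example, the control rate is 0.05 + 0.95 × 0.10 = 0.145 and the difference is 0.95 × 7 = 6.65 points. Expected control events among 81 rise from 8.1 to 11.7.

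**Separating the two effects.** If the planners keep the 7-point target and take only the control rate from this study, total N at 80% power goes from 746 to 944 at c = 5%. Using the diluted difference as well takes it to 1038 (2 × 519).

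**Against sampling error.** The 95% half-width for a 10% rate in 81 people is 1.96 × √(0.10 × 0.90 / 81) = 6.5 points. The shift at c = 5% is 4.5 points, so it lies within random error. It is nevertheless a shift in one direction, which a larger sample would not remove.

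**The case against.** Several points on the other side stand and limit the finding.

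- **Who is affected.** A reader might picture a client two weeks into a quit programme who joins and is then recorded as a 4-week quit. The documents do not support that as the typical case: entry is for current smokers (4.2, 4.4), and the background defines a 4-week quit by abstinence after a quit date, so that client would normally have stopped. The group is narrower: booked and not yet seen, seen before the quit date, or lapsed.
- **Where they come from.** A reader might also infer that the study recruits from service providers. Section 4.7 names pharmacists and GP practices as types of provider; it does not say that the recruiting sites deliver the service. GP recruitment works from lists of smokers, and most named community sites are not pharmacies.
- **How many.** The background says that services reach 5–10% of smokers. If that is reach over a period, which is not stated, the share in contact on a given day would be smaller, although recruitment could select for or against them. Service-record events also need a yes to the staff prompt and consent (4.9.2), so counting every such person is a worst case.
- **What is already collected.** Earlier SSS use at baseline and the question on what prompted the booking could expose some cases. The items are in Appendix E, which is not shown. But 4.12 attaches no rule to either.
- **Scope.** Counting rules are often left to an analysis plan, which may exist. Eligibility, the baseline items and the content of the service report are set in this protocol, and a later rule on dates cannot work if the dates are not requested.
- **Same criteria later.** A definitive trial with identical entry and outcome rules would meet the same dilution, so its sample size would be consistent with its own design. That carries an avoidable loss of power forward rather than removing it.

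**Conclusion.** The point holds in a limited form. As written, a booking or contact that predates randomisation can count as an event in either arm. If any such participants enter, both rates are inflated and the difference is multiplied by (1 − c). The direction is certain. The size is not, because the protocol gives no value for c and the 10% and 17% rates are assumed: the control rate would read 10.9% at c = 1%, 11.8% at 2% and 14.5% at 5%. Section 4.12 also brings clinical significance into the sample size, so the observed difference is not its only driver.

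Two stronger readings are not supported. There is no systematic bias between arms, since 1:1 randomisation spreads these participants evenly on average; chance imbalance is possible with about 81 per arm. The feasibility decision is not undermined either: the primary objective (3.2) and the stop/go criterion (section 6) rest on recruitment and attrition, which are little affected. What is at risk is the secondary event-rate estimate, and it can be protected cheaply.

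**What to change.** - **4.4 and 4.10.1:** keep past users eligible. Add one baseline item asking whether the participant is now receiving SSS support or holds a future appointment.
- **4.9.2:** request booking and attendance dates in the service report. Compare them with the participant's randomisation date. The joining date and time are already stored; the time of allocation should be stored too, because the baseline questionnaire comes between the two.
- **4.10.2 and 4.12:** count towards the event rate and the between-arm difference only bookings made after randomisation and attendances arising from them. Word the follow-up question to match. Report participants with service contact at entry separately, by arm.

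Excluding those participants is optional. The protocol wants recruitment that resembles real-world use, and a flag with separate reporting protects the estimate without narrowing entry.

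The cost is one question, date fields in a report already being obtained, short wording changes, and slightly fewer counted events.

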4.5 Exclusion Criteria

Via self-assessment, smokers who do not understand written English or are under 16 years of age, will be excluded from taking part.

4.6 Randomisation

Randomisation will be carried out through the study website during months 10-14 of the study. For this purpose, a digital bespoke randomisation tool (embedded within the study website) will be developed in collaboration with our statistician [name] and with oversight by the Clinical Trials Unit (CTU) at the University of Warwick. This will auto-randomise at the individual level (1:1) using minimisation to ensure balance. Via the study website (hosted by eNgage – see below), the research team will have access to a table that presents live data on condition assignment; NB. the research team will be blind to condition assignment – just condition A and B will be presented. Please see procedure below (section 4.9) for further detail on how and when randomisation occurs.

4.7 Intervention

The StopApp is a web-based self-administered interactive intervention designed to address the barriers that smokers typically face in accessing SSSs. In brief, the intervention comprises 1) an introduction to StopApp. 2) collection of information about age, gender, previous attempts to guit and previous use of SSSs in order to tailor content accordingly. Age and gender are used to provide messaging from similar others to enhance perceptions that 'people like me use SSS'. Information about previous guit attempts and use of SSSs is used to tailor the way in which the subsequent content is framed, 3) StopApp then provides users with information about what SSSs are like, to address negative perceptions many smokers have about what the service offers and how they will be treated. Infographics and messages from real SSS users are used to try to keep textual information minimal and enhance positive norms about who uses SSS. 4) Throughout engagement, the option to go straight to booking an appointment is provided in case people are already motivated to do this. 5) Users are then provided with a list of other potential barriers to SSS access that they may have and can select as many as apply. This then determines which further content is supplied which addresses 6) practical barriers 7) fears about trying and failing and 8) beliefs that needing support to stop smoking is a 'weakness'. At the end of the process users have the option to either 9) book an appointment or 10) get a reminder to re-access the intervention one month later, if they feel they are not yet ready. We have appended an example route through the StopApp (see Appendix F) to illustrate the content. It is linked to the on-line outcomes reporting systems (PharmOutcomes and Outcomes4Health) used by SSSs in Warwickshire (and many other local authority areas across the UK). PharmOutcomes is used by pharmacists and others offering stop smoking services. Outcomes4Health is used by GP practices offering SSS appointments. These secure systems support service providers in recording information about what they have provided to a service user and the outcomes associated with this, including whether or not a quit date was set and whether or not a CO verified 4 week guit rate was achieved by a service user.

The StopApp is a website, so requires internet access for use (i.e. it is not downloaded to the user's device), but is optimised for use on smartphone and tablet devices. It therefore has the feel of an 'app' with content and features that look

appealing on a small screen device. We developed the intervention in collaboration with the Tobacco Control lead at Pubic Health Warwickshire.

As well as applying co-production and usability methods (further detailed below) the content of the StopApp intervention was systematically developed using the Behaviour Change Wheel approach (Michie et al., 2014), which is underpinned by a model of the determinants of behaviour; the COM-B model (Michie et al., 2011) and maps onto to the theoretical domains framework (Cane et al., 2012). In applying the COM-B, StopApp aims to increase the capability and motivation (C and M from COM-B) of smokers to access support to stop smoking and then provides the opportunity (O from COM-B) to book an appointment instantly at a convenient time and location for the user (our target **B** - **behaviour**), and with text message or email confirmation and reminders to attend the appointment (a further target behaviour). Applying the COM-B allowed us to map identified barriers to service access with intervention functions and behaviour change techniques (BCTs) most likely to address those barriers. Specific content within the app delivers 19 BCTs identified as most useful for supporting SSS access behaviour (Fulton et al., 2016). For example, the BCT 'Provide information about social/environmental consequences' was identified as one of several that can improve 'Psychological Capability' to access SSSs. Application of this BCT occurs more than once, but an example relating to psychological capability and the theoretical domain of 'knowledge' includes providing information about the benefits of SSS, about what they do, how they have helped others, and what they offer including that you can have more than just one appointment.

The control group will receive access to a web-based pdf 'leaflet', hosted online which is part of Warwickshire's standard stop smoking service provision and containing much of the same information about services: see 'Quit4Good' Service Leaflet (Appendix G). The leaflet does not link to an on-line booking system and does not provide tailored routing according to the types of barriers a smoker may have to SSS access. It has not been systematically designed to address barriers to service access and is not underpinned by a theory of behaviour change or identified BCTs.

